8.2.3 Mechanistic endpoints

- Seroconversion to COV
- Host immune cell profile grouped who test respectively positive or negative to COV during an ARI, including LRI, and stratified by treatment (COV⁺/OM⁺, COV⁺/OM⁻, COV⁻/OM⁺, COV⁻/OM⁻).
- White blood cell transcriptomic profile by group (COV⁺/OM⁺, COV⁺/OM⁻, COV⁻/OM⁺, COV⁻/OM⁻).
- White blood cell cytokine production profile by group (COV⁺/OM⁺, COV⁺/OM⁻, COV⁻/OM⁺, COV⁻/OM⁻).

8.2.4 Safety endpoints

- Treatment-related adverse events.

- Routine haematology and clinical chemistry.

8.3 Stopping Rules

Study enrolment may be stopped if death of a participant that is related to the study treatment occurs.

Safety data will be presented by group in a blinded fashion to the Data Safety and Monitoring Board (DSMB) at scheduled DSMB meetings during the trial. The DSMB will have the authority to request un-blinded data if necessary. The DSMB may recommend that enrolment or study treatment be discontinued for the safety of participants.

Resumption of the study will be contingent upon a favourable decision by the Sponsor, and the DSMB after review of the adverse event data.

9. Selection and withdrawal of participants

Deviations from the eligibility criteria will not be permitted as they may potentially jeopardise patient safety and the scientific integrity of the study.

9.1 Inclusion criteria

Participants who meet *all* of the following criteria are eligible for enrolment:

1. HCW in front line clinical departments assessing or caring for patients with suspected or verified COV infection in one of the recruiting hospitals in Brisbane or the UK,
2. Participants who, in the opinion of the investigator, are able to comply with the protocol for its duration,
3. Written informed consent signed and dated according to local regulations.

9.2 Exclusion criteria

Participants who meet *any* of these criteria are *not* eligible for enrolment:

- Staff with prior COV infection necessitating workforce removal

9.3 Criteria and procedures for participant withdrawal

9.3.1 Withdrawal of participants from study

Participants will be withdrawn from the study if any of the following conditions are met:

- The participant withdraws their consent
- The participant fails to return to the clinic (i.e., they are lost to follow-up or death)
- The site investigator or his/her designee believes that continuation in the study is no longer in the participant's best interests (which may be as a result of the occurrence of adverse events (AE) or clinically relevant laboratory results)
- The participant is unable to comply with the protocol, including completing required study treatments, procedures, tests and/or examinations
- The Sponsor reserve the right to terminate the entire study or any participants involvement at any time

Participants who prematurely discontinue investigational product will be encouraged to continue with the study visit schedule and assessments. For further information regarding Early Withdraw Visits refer to Section 10.4.

Those participants that cease the investigational product before the end of the study, but continue to be assessed for all other aspects of the study, will be regarded as members of the intention to treat (ITT) sample. All remaining study medication (including used and unused medication and packaging) will be collected.

In all cases, the reason and date of withdrawal from the study, or investigational product, will be completed in the source documentation and the CRF. If the withdrawal is due to an adverse event or a clinically significant laboratory result, the participant will be followed until the AE is resolved or is clinically stabilised. The AE or laboratory result must be recorded in the CRF.

If a participant tests positive to a clinical test (not part of the study) they will follow the hospital isolation protocol. The study Covid testing is done by measuring antibodies, which are not suitable for acute surveillance as it detects past infection. Results (positive or negative) will be returned to participant for their own information

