10.3 Early withdrawal visit

Participants who discontinue from the study for reasons other than ARI necessitating workforce removal, will be asked to attend an Early Withdrawal Visit. Where practicable, the study procedures scheduled for the current visit should be completed, or in the case of early withdrawal between visits, the procedures scheduled for the next study visit should be completed if the participant is agreeable.

For safety follow-up, participants should be encouraged to provide a blood sample. All used and unused study medication (including packaging) should be collected or arrangements made for its return to the clinic at this visit. Where possible, stop dates for ongoing AEs should be obtained.

11. Study treatment

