11.1 Enrolment and randomisation

Once all required screening assessments are completed and eligibility is confirmed, participants will be registered with the Sponsor. Upon approval of registration, participants will be assigned a unique participant number that will remain consistent for the duration of the study.

Participants who sign an informed consent form, but do not fulfil the inclusion/exclusion criteria, will not be allocated a participant identification number.

Participants will be randomised into one of the following two groups on a 1:1 ratio with 500 participants per group:

- Group 1 (WLC): OM85 7.0 mg will be given daily for three months from Month 3
- Group B (Initial Treatment): OM85 7.0 mg will be given daily for three months from Day 0

Please see the Study Reference Manual for randomisation instructions.

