11.6 Permitted medications during study

During the study, participants will be allowed to take medications routinely used in the management of fever, cough or wheezing attacks, including inhaled and oral steroids. All medications will be recorded in the source documentation and CRF.

12. Assessment of safety

The site investigator is responsible for the assessment and documentation of any event that meets the criteria of an AE (see Section 12.1) or an SAE (see Section 12.2).

AEs and SAEs will be collected from the time of first dose of investigational product until the participant has completed the study at their final visit, even if the participant ceases the investigational product prematurely.

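### Section 9.3.1 withdraws from the study anyone unable to complete study treatment, which conflicts with its own retention text and, before Month 3, can act on Group 2 only

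*Combined protocol and SAP*

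**What the plan says.** The list in Section 9.3.1 opens with a mandatory stem: "Participants will be withdrawn from the study if any of the following conditions are met". One condition is "The participant is unable to comply with the protocol, including completing required study treatments, procedures, tests and/or examinations".

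The paragraph after the list points the other way: "Participants who prematurely discontinue investigational product will be encouraged to continue with the study visit schedule and assessments". The next one covers people who stop product and says that those who stop "but continue to be assessed for all other aspects of the study, will be regarded as members of the intention to treat (ITT) sample". The opening of Section 12 collects adverse events "until the participant has completed the study at their final visit, even if the participant ceases the investigational product prematurely", which presumes that such a person is still in the study.

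On timing, Section 11.1 says "Group 1 (WLC): OM85 7.0 mg will be given daily for three months from Month 3", while Group 2 starts on Day 0. Section 13.3.1 bases the primary comparison on data gathered before Group 1 starts treatment. Section 13.2.1 defines the intention-to-treat group as randomised participants with at least one dose. Section 9.4 says that those who leave are not replaced.

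**The concern.** A site whose participant cannot go on with the capsules has two instructions. The list says the person must leave the study. The following paragraph says the person should be encouraged to stay. No criterion tells the site which applies.

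The conflict matters more here than in a placebo-controlled trial. The control arm is an untreated wait list, so during the primary window only one arm has treatment to fail. If sites follow the list literally, outcome data are lost in Group 2 for a reason that has no counterpart in Group 1 and may be related to health or adherence. Randomisation no longer protects a comparison of those who remain, and the error can go in either direction.

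**Working it through.** **1. Are the texts compatible?** The stem in 9.3.1 is mandatory and any one condition is enough. Inability to complete study treatments is named within one of them, and the consequence is withdrawal from the study, not from product. Encouragement to attend visits cannot operate for someone who has to be withdrawn. The texts conflict.

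**2. Which arm does it reach?** From Day 0 to Month 3, scheduled study treatment exists in Group 2 only (11.1), and this is the primary window (13.3.1). Procedures, tests and examinations can be missed in either arm; daily SMS reporting, for example, follows randomisation in both (10.1.7). So only the treatment part is one-sided. Two exceptions are minor for the planned comparison: the DSMB may consider moving Group 1 to OM85 after the month 1 interim analysis (13.2.2), and the visit window allows a start up to 5 days early (10.2).

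**3. The plan's own figures.** Section 13.2 gives no withdrawal allowance. Its power figures provide the inputs of 20% risk and 1000 per group. With power = Φ((d − 1.96·SE₀)/SE₁), two-sided α = 0.05 (sidedness is not stated), SE₀ pooled and SE₁ unpooled:
- 500 per group, 20% vs 13.5%: (0.065 − 1.96 × 0.02362)/0.02353 = 0.795, power 78.7% (stated 80%).
- 1000 per group, 20% vs 15%: (0.050 − 1.96 × 0.01699)/0.01696 = 0.985, power 83.8% (stated 80%).

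Losing 10% of Group 2 lowers the second figure to 81.7%, and losing 20% lowers it to 79.1%. Power is not the main issue.

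**4. Possible bias, by assumption.** Take no drug effect, 20% risk in both arms, 1000 per group, and withdrawn participants excluded. Let f be the share of Group 2 withdrawn and r their risk relative to those retained. The retained risk is x = 0.20/(f·r + 1 − f), and the observed risk ratio is x/0.20. The false-positive rate is Φ(z − 1.96) + Φ(−z − 1.96), with z = (0.20 − x)/√(0.16/1000 + x(1 − x)/(1000(1 − f))).

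The lower value of f is the adult count in Section 6.3, 5/142 = 3.5% discontinuing on active product. It comes from patients with COPD or chronic bronchitis, so it is a limited guide. The placebo count there, 9/131 = 6.9%, lies inside the range. The upper value of 10% and all values of r are assumptions.

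| f | r | x | Risk ratio | False-positive rate |
|---|---|---|---|---|
| 3.5% | 0.5 | 20.4% | 1.02 | 5% |
| 3.5% | 1 | 20.0% | 1.00 | 5% |
| 3.5% | 1.5 | 19.7% | 0.98 | 5% |
| 3.5% | 2 | 19.3% | 0.97 | 7% |
| 3.5% | 3 | 18.7% | 0.93 | 11% |
| 10% | 0.5 | 21.1% | 1.05 | 9% |
| 10% | 1 | 20.0% | 1.00 | 5% |
| 10% | 1.5 | 19.0% | 0.95 | 8% |
| 10% | 2 | 18.2% | 0.91 | 17% |
| 10% | 3 | 16.7% | 0.83 | 47% |

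Last row in full: x = 0.20/(0.30 + 0.90) = 0.1667; SE = √(0.000160 + 0.000154) = 0.01773; z = 0.0333/0.01773 = 1.88; Φ(−0.08) = 0.47. For f = 10% and r = 0.5, nearly all the rejections go against OM85.

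**5. If they are counted instead of excluded.** Suppose the withdrawn stay in the denominator, leave halfway through at ordinary risk, and count as event-free afterwards. With f = 10% the observed Group 2 risk is 0.90 × 0.20 + 0.10 × 0.10 = 0.19, a risk ratio of 0.95. The counting rule therefore matters even without a risk gradient, and the plan does not state one.

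**The case against.** The best defence is that the protocol already separates stopping product from leaving the study. Section 9.3.1 records the two as alternatives, Section 11.4 lists withdrawal and non-compliance as different states, Section 12 keeps collecting adverse events after product is stopped, and the 80%-of-doses rule for the per-protocol group presupposes less adherent people who remain. On that view the condition is meant for someone who cannot follow the protocol at all. This is good evidence of what the sponsor intends. It does not cancel a mandatory condition that names study treatments, so the conflict stands.

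Other parts of the defence succeed against stronger readings that a reader might infer:

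- *That leavers drop out of the intention-to-treat group.* Section 9.3.1 says that people who stop but stay are members; it does not say that those who leave are not. Section 13.2.1 does not require continued assessment. Membership does not supply a missing outcome, however.
- *That an ARI ends follow-up.* Section 10.3 speaks of "Participants who discontinue from the study for reasons other than ARI necessitating workforce removal", which may look as if the primary event were a reason to leave. ARI is not among the conditions in 9.3.1, no section ends follow-up at an ARI, and an unscheduled visit is provided for it. The natural reading is that someone leaving because of an ARI needs no additional Early Withdrawal Visit.
- *That the whole condition acts on Group 2 only.* Only its treatment part does.
- *That a large false-positive rate is to be expected.* The upper end needs 10% withdrawn at three times the risk, neither of which the documents give. The calculation also has every such person leave and ignores ARIs recorded before departure or at the Early Withdrawal Visit.

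**Conclusion.** The contradiction in Section 9.3.1 is certain, and in the primary window the treatment part of the condition can take participants and their outcomes from Group 2 alone. The size and direction of any resulting bias cannot be determined from the documents. The illustrated range is wide because its inputs are assumed; at the 3.5% discontinuation seen in Section 6.3, the false-positive rate stays between 5% and 11%. The documents do not support a claim that the trial will be biased in favour of OM85, or that follow-up stops at an ARI. The point should be corrected because a small edit removes an avoidable arm-specific loss of data. It does not show that the primary analysis is invalid.

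**What to change.** Reconcile the two texts in Section 9.3.1:

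- Remove study treatments from the study-withdrawal condition, leaving procedures, tests and examinations.
- State that stopping or missing product does not by itself end outcome follow-up: daily SMS and scheduled visits continue unless consent is withdrawn or another listed withdrawal condition applies.
- Align the intention-to-treat sentence in 9.3.1 with the definition in 13.2.1, which does not depend on continued assessment.
- Optionally, clarify in 10.3 that an ARI with workforce removal is an endpoint and does not itself end follow-up. In the same edit, correct the reference in 9.3.1 to Section 10.4, since the early withdrawal visit is in 10.3.

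Rules for stopping product are not affected. The cost is wording, plus SMS contact and visits already scheduled for people who stop the capsules.

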9.3.2 Premature termination of study/closure of centre

The Sponsor or the Therapeutic Goods Administration (TGA) may stop the study for any reason. They may also prematurely close any study centre following consultation with the parties involved.

In the event that the study is terminated prematurely, written notification must be sent to the ethics committee (EC), according to local regulations. The site investigator must also promptly inform all study participants and if appropriate, should assure appropriate medical follow-up. All study materials, except those documents that must remain on site, should be returned to the sponsor.

9.4 Replacement of participants

Participants who withdraw consent or who discontinue the study for any reason will not be replaced.

10. Study procedures

The study procedures are listed in the Schedule of Assessments and Procedures in Appendix 1.

10.1 Description of assessments and procedures

Procedures conducted as a part of the participant's routine clinical management and obtained prior to informed consent may be used for screening purposes or assessing eligibility. However, the procedure must meet the protocol-defined criteria and have been performed within the timelines permitted by the protocol.

10.1.1 Informed consent

A signed, written informed consent must be obtained from the participant and will be undertaken prior to any study-specific assessments or procedures. In accordance with Good Clinical Practice (GCP) guidelines, informed consent is an ongoing process throughout the study.

10.1.2 Eligibility criteria

To be eligible for enrolment into the study, participants must meet *all* the inclusion criteria and *none* of the exclusion criteria.

10.1.3 Medical/ work history

A comprehensive general medical history will be taken by the site investigator to determine significant previous and current medical conditions, diseases, procedures and surgeries that may increase the risk of developing a ARI necessitating workforce removal. Exposure data, including time on the front line, also be collected.

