6.1.2 Health Care Workers

HCW are at the forefront of the Covid pandemic. Figures from China show around 3300 HCW were infected, as were 20% of Italy's HCW¹. Infected HCW who develop lower respiratory illnesses (LRI) are removed from frontline services putting additional pressure on system ability to provide patient care. Respiratory viruses, including COV, are initially encountered by the nasal epithelium where infection is initiated. An adequate anti-viral response can contain the virus in the upper airway, with cold-like symptoms. An inadequate response can see the infection spreading to the lower respiratory tract and induce a severe lower respiratory illness (sLRI). HCW in front line clinical departments, such as emergency departments, intensive care units, COV isolation wards and radiology departments, are at increased risk of COV infection.

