10.2 Scheduled visits

This study consists of 5 visits (Group 1 - WLC) or 4 visits (Group 2 – initial treatment) over 6 or 9 months respectively (see Figure 1) Study procedures to be performed at each visit are detailed in the Schedule of Assessments and Procedures in Appendix 1.

Visits should be conducted within the specified visit windows where possible.

Figure 1: Study timeline and procedures. Nasal swab collection (blue arrow), blood collection (red arrow).

Group 1 (WLC)

Visit 1 – Screening and randomisation

The following assessments and procedures will be performed and recorded at this visit:

- Obtain written informed consent
- Evaluate inclusion and exclusion criteria
- Obtain demographic history
- Obtain medical history
- Vital signs
- Explain daily respiratory symptom data collection and assist with collection for Day 0

Once all screening procedures have been completed and eligibility confirmed, the participant will be registered with the Sponsor. Further information on the registration process is provided in the Study Reference Manual.

Visit 2: Treatment initiation 3 months post randomisation (±5 days)

- Update demographic & medical history
- Vital signs

- Nasal swab
- Collection of blood samples
- Dispense study medication and explain administration
- Adverse event assessment

Visit 3: Treatment cessation 6 months post randomisation (± 5 days)

- Vital signs
- Nasal swab
- Collection of blood samples
- Clarify any missing data (daily respiratory symptoms) with participant, if not previously addressed by email/SMS
- Adverse event assessment
- Collect used investigational product packaging and unused investigational product

Visit 4: Follow up cessation 9 months post randomisation (± 5 days)

- Vital signs
- Nasal swab
- Collection of blood samples
- Clarify any missing data (daily respiratory symptoms) with participant, if not previously addressed by email/SMS
- Adverse event assessment

Unscheduled Visit: at time of ARI necessitating workforce removal

- Vital signs
- Nasal swab
- Collection of blood samples
- Clarify any missing data (daily respiratory symptoms) with participant, if not previously addressed by email/SMS
- Adverse event assessment

Group 2 (Initial Treatment)

Visit 1 – Screening, randomisation, and treatment initiation

The following assessments and procedures will be performed and recorded at this visit:

- Obtain written informed consent
- Evaluate inclusion and exclusion criteria
- Obtain demographic history

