- Obtain medical history
- Vital signs
- Nasal swab
- Collection of blood samples
- Drug delivery
- Dispense study medication and explain administration
- Explain daily respiratory symptom data collection and assist with collection for Day 0

- Adverse event assessment

Once all screening procedures have been completed and eligibility confirmed, the participant will be registered with the Sponsor. Further information on the registration process is provided in the Study Reference Manual.

Visit 2: Treatment cessation 3 months post randomisation (± 5 days)

- Vital signs
- Nasal swab
- Collection of blood samples
- Clarify any missing data (daily respiratory symptoms) with participant, if not previously addressed by email/SMS
- Adverse event assessment
- Collect used investigational product packaging and unused investigational product

Visit 3: Follow up cessation 6 months post randomisation (± 5 days)

- Vital signs
- Nasal swab
- Collection of blood samples
- Clarify any missing data (daily respiratory symptoms) with participant, if not previously addressed by email/SMS
- Adverse event assessment

Unscheduled Visit: at time of ARI necessitating workforce removal

- Vital signs
- Nasal swab
- Collection of blood samples
- Clarify any missing data (daily respiratory symptoms) with participant, if not previously addressed by email/SMS
- Adverse event assessment

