13.1 Randomisation, stratification and blinding

Participants will be randomised to the wait list group (Group 1) or the initial intervention group (Group 2) using a one-to-one ratio, stratified by Country (Australia, UK), hospital (QCH, PA, TPC) and department [High risk (ED, ICU, isolation wards), lower risk (radiology, general wards, other)].

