13.2 Sample size calculations

There are no data in the literature on use of OM85 for the primary prevention of ARI, in relation to COV. However, 20% of Italy's HCW are infected with COV¹. If we assume 20% infection in Gp 1, then with 500 HCW in each group we will be able to detect a reduction in ARI in Gp 2 by 32.5% (to 13.5%) with 80% power ($\alpha=0.05$). Combined with 1000 UK-recruited HCW, we will be able to detect a 25% reduction (80% power, $\alpha=0.05$).

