13.2.2 Statistical analyses

The *interim analysis*, undertaken at month 1 on both the "intention-to-treat" and "per protocol" groups, will examine the primary outcome: if the treatment difference is statistically significant in favour of OM85 the DSMB will consider immediately switching WLC participants to OM85.

Between-group differences in the primary outcome at 3 months will be assessed using log-binomial regression. Secondary outcomes measured to follow-up cessation will be assessed using mixed-effects models with group and stage (treatment/follow-up) (main effects and interaction) as fixed effects and HCW as random effect. Time-to-ARI analyses will use the log-rank test. Analyses will be undertaken on both the "intention-to-treat" and "per protocol" groups.

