13.3.1 Primary efficacy endpoint

The primary endpoint, defined in Section 7.2.1, will be analysed 3 months after enrollment using data collected prior to the WLC group commencing treatment, by comparing between-group differences in rates of ARI that necessitated workforce removal. The primary analysis will be conducted using log-binomial regression on both the "intention-to-treat" and "per protocol" groups.

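### The primary analysis does not say whether it adjusts for front-line exposure, which the plan collects with the Visit 1 history; specifying this now would give a small gain in precision

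*Combined protocol and SAP*

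**What the plan says.** Section 10.1.3 (Medical/ work history) has two parts. The first describes a general history of conditions and procedures that may raise the risk of an ARI with workforce removal. The second is a separate sentence: "Exposure data, including time on the front line, also be collected". It gives no visit, unit, reference period or purpose.

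In section 10.2, Visit 1 for both groups includes "Obtain medical history". Only Group 1 has a later entry, at month 3: "Update demographic & medical history". Appendix 1 agrees on the medical history: Visits 1 and 2 for Group 1, Visit 1 alone for Group 2. Neither place lists work history or exposure as its own item.

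For the primary endpoint, section 13.2.2 says: "Between-group differences in the primary outcome at 3 months will be assessed using log-binomial regression". Section 13.3.1 repeats this: "The primary analysis will be conducted using log-binomial regression on both the" intention-to-treat and per-protocol groups. Neither names a covariate. For the secondary outcomes, the same sections do list model terms: group, stage, their interaction and a random effect for the participant.

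Exposure enters the design in coarse form. Section 13.1 stratifies randomisation by country, hospital and a two-level department risk (high or lower).

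**The concern.** How long and how intensively someone works at the front line could plausibly predict a respiratory infection that takes them off work. If a pre-randomisation measure of this is available for every participant, a prespecified adjustment normally buys some precision and reduces the influence of chance imbalance. The plan arranges to collect the information but does not say whether the primary analysis will use it.

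The silence also leaves open which value an analyst might choose later. Time on the front line accrued during the three-month comparison period is affected by the outcome, because workforce removal shortens it. If the month 3 history update covers exposure, that value would exist in Group 1 only. Adjusting for either could bias the treatment effect.

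**Working it through.** **Inputs from section 13.2.** "If we assume 20% infection in Gp 1, then with 500 HCW in each group", a fall to 13.5% is detectable with 80% power at alpha 0.05. With the UK participants added (1000 per group), a 25% reduction is detectable, which is 20% to 15%. Sidedness is not stated; two-sided is assumed. Allocation is 1:1, with no dropout allowance.

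**Step 1: reproduce the plan's power.** With p̄ = (p1 + p2)/2:

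power = Φ{ [ |p1 − p2|·√n − 1.96·√(2p̄(1 − p̄)) ] / √(p1(1 − p1) + p2(1 − p2)) }

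- 500 per group, 0.20 v 0.135: (1.453 − 1.035)/0.526 = 0.795, power 78.7%. Reaching 80% needs 517 per group.
- 1000 per group, 0.20 v 0.15: (1.581 − 1.053)/0.536 = 0.985, power 83.8%.

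Both are close to the stated 80%.

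**Step 2: value of a baseline covariate.** If it explains a share R² of the outcome variance, effective n = n/(1 − R²). The documents give no R² and no risk ratio for exposure. The odds ratio (OR) per standard deviation (SD) of exposure is therefore assumed over a range, with R² averaged over the two arms.

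| Assumed OR per SD | 500 per group: R², effective n, power | 1000 per group: R², effective n, power |
|---|---|---|
| 1.0 | 0, 500, 78.7% | 0, 1000, 83.8% |
| 1.25 | 0.0069, 503, 79.0% | 0.0071, 1007, 84.0% |
| 1.5 | 0.0224, 511, 79.6% | 0.0232, 1024, 84.6% |
| 2.0 | 0.0630, 534, 81.2% | 0.0650, 1070, 86.1% |
| 3.0 | 0.1422, 583, 84.5% | 0.1457, 1171, 89.0% |

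At an OR of 2.0 the gain is 81.2 − 78.7 = 2.5 points, or 86.1 − 83.8 = 2.3 points. Up to 1.5 it is under 1 point.

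A second illustration assumes three equal exposure tiers with risks of 10, 20 and 30%. The between-tier variance is (0.01 + 0.04 + 0.09)/3 − 0.04 = 0.0067, and 0.0067/0.16 = 4.2%, worth about 4% more participants.

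These shares are of total variance. If the strata are already in the model, the relevant ratio is (1 − R² of strata)/(1 − R² of strata plus exposure), which is smaller when exposure tracks department risk.

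**Step 3: check by simulation.** With 1000 per group, 20% v 15% and 400 trials per setting, the unadjusted risk ratio was compared with one standardised from a logistic model. Relative efficiency was 1.00, 1.03, 1.10 and 1.27 for ORs of 1.0, 1.5, 2.0 and 3.0. These ratios are rough: at 3.0 the formula gives 1171/1000 = 1.17. The first value shows no loss when the covariate has no predictive value.

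**Step 4: does the planned model tolerate the covariate?** In the same simulated trials, a normally distributed covariate was added to the log-binomial model with default fitting. Fits failed or gave out-of-range probabilities in 0%, 9.5%, 56% and 99% of trials. The data were generated from a logistic model, so the rates are illustrative, but failure rises with predictive strength.

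**Step 5: what if the wrong exposure value is used?** In an illustrative simulation (true risk ratio 0.75, assumed 14-day removal), adjusting for front-line days accrued after randomisation moved the estimate from 0.76 to 0.81.

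**The case against.** The strongest case against is that the plan does not confirm a baseline exposure value at all. Section 10.1.3 gives no time point, whereas section 10.1.4 fixes the demographic items at Visit 1, and the visit lists mention only medical history. Nor is there evidence that past time on the front line predicts a future ARI. Section 6.1.2 says that staff in front-line departments "are at increased risk of COV infection", but that concerns department type, every participant works in such a department, and the two-level department risk is already a stratum. Excluding staff with a prior COV infection that led to removal makes even the direction uncertain. On this view, choosing one undefined variable is a reviewer's preference.

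Much of this stands. It limits the size of the point and means that the variable must be defined before it can be used. It does not remove the point: the medical/work history is one section, Visit 1 is its natural place, and the simulated adjustment lost no efficiency when the covariate was uninformative.

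A reader might infer more than the text allows:
- *That the primary model contains treatment group only.* The sections are silent on covariates. Silence is not a stated unadjusted model.
- *That exposure is collected because it predicts the endpoint.* The risk clause in section 10.1.3 describes medical conditions and procedures. The exposure sentence gives no reason.
- *That precision is being given up at no cost.* The amount is unknown, and step 4 shows that the planned model may not accept a continuous exposure term.
- *That adjustment would offset the open-label design.* It addresses chance baseline imbalance, not behaviour that changes once allocation is known.

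**Conclusion.** The point holds as a minor, optional improvement. The plan intends to collect front-line exposure, and the visit schedule points to Visit 1 in both groups, but the primary analysis names no covariates. An unadjusted comparison would remain valid under randomisation, and no stated figure in the plan changes.

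The gain is probably small: about 0 to 2.5 points of power for an assumed OR per SD of 1.0 to 2.0, before any reduction for overlap with the strata. A larger gain (5.2 to 5.8 points) needs an OR of 3.0, for which the documents offer no support. The result rests on three assumptions: a two-sided test at 0.05, the plan's event rates, and an exposure value recorded before randomisation.

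The clearer omission is that the randomisation strata, which already carry part of the exposure information, are not stated to be in the primary model. The same change settles both.

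**What to change.** **Section 10.1.3, section 10.2 and Appendix 1.** State that front-line exposure is recorded at Visit 1 before randomisation in both groups. Define it, for example as time on the front line over a stated period in prespecified categories, and list it in the visit schedule.

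**Sections 13.2.2 and 13.3.1.** State that the primary marginal risk ratio is estimated by standardisation from a logistic working model with group, the randomisation strata (country, hospital, department risk) and the Visit 1 exposure value. Name the method for its confidence interval. Give a rule for missing exposure values that does not depend on group or outcome. State that exposure recorded after randomisation, including any Group 1 update at month 3, is not used in this model.

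**Cost.** Protocol and SAP wording, one defined CRF item and slightly more analysis work. No new visit, sample or participant is needed. It should be settled before any outcome data by group are seen, including at the month 1 interim analysis.
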